The relationship between exposure (in CSF, plasma) of elenbecestat with potential biomarkers of Alzheimer's disease as deemed appropriate will be evaluated using appropriate statistical model with the continuous changes in biomarker at 24 months as response variables and exposure variables (in CSF, plasma) of elenbecestat as independent variables.

Analyses for Exploratory Efficacy Endpoints

Time to change of concomitant AD treatment will be analyzed similarly to that for time to conversion to dementia based on clinical diagnosis. Time to change of concomitant AD treatment is defined as time from randomization to the first dose increase and/or initiation of treatment with AChEI or memantine after randomization. For subjects without any change of concomitant AD treatment by the end of study, the time to change of concomitant AD treatment will be censored at the date of last assessment of concomitant medication.

The proportion of subjects with any change of concomitant AD treatment at 24 months will be analyzed similarly to that for proportion of subjects with dementia diagnosis at 24 months.

The rate of change over time (mean slope) based on change from baseline in the NPI-10 item will be analyzed in a manner similar to that used for the rate of change over time (mean slope) based on

change from baseline in the CDR-SB.

The analysis of the following exploratory efficacy endpoints will be performed to compare elenbecestat versus placebo using the appropriate prespecified statistical methods including MMRM model, analysis of covariance model (ANCOVA), etc. For each exploratory efficacy endpoint, the treatment effect for elenbecestat 50 mg per day versus placebo will be tested at a significance level of 2-sided $\alpha=0.05$.

- Change from baseline in NPI-10 item at 24 months
- Change from baseline in EQ-5D (subject self-reported, study partner self-reported, and subject measured by proxy) and QOL-AD (subject and study partner) at 24 months
- Change from baseline in Zarit's Burden Interview at 24 months

Additional analyses may be performed as needed.

Pharmacokinetic, Pharmacodynamic, Pharmacogenomic, and Other Biomarker Analyses

Pharmacokinetics

Safety Analysis sets will be used for individual elenbecestat plasma and CSF concentration listings. The PK Analysis Set will be used for the summaries of elenbecestat plasma and CSF concentrations.

A population PK approach will be used to characterize the PK of elenbecestat. The effect of covariates (ie, demographics) on elenbecestat PK will be evaluated. The PK model will be parameterized for clearance (CL) and volumes of distribution. Derived exposure parameters such as area under the concentration \times time curve (AUC) will be calculated from the model using the individual posterior estimate of CL and dosing history.

Pharmacokinetic-Pharmacodynamic

The PK/PD relationship between CSF biomarker levels and plasma PK parameters or CSF concentrations of elenbecestat will be explored graphically and any emergent relationship will be explored through population PK/PD modeling. These PK parameters include maximum observed concentration (C_{max}), and $AUC_{(0-24)}$ derived from the population PK model. The PK/PD relationship between plasma PK parameters and CSF concentrations of elenbecestat with other biomarkers may also be explored using similar methods.

Additionally, the relationship between various PK parameters (eg, C_{max}) or CSF concentrations of elenbecestat and CDR-SB at 24 months, and the relationship between various PK exposure parameters or CSF concentrations of elenbecestat and the change from Baseline for 24 months in ADAS-cog14, and the MMSE, will be explored graphically. Any emergent relationships will be explored through population PK/PD modeling. The relationship between exposure to elenbecestat and most frequent AEs will also be explored.

Safety Analyses

Evaluations of safety will be performed on the Safety Analysis Set. The incidence of AEs, out-of-normal-range laboratory safety test variables, abnormal ECG findings, and out-of-range vital signs, suicidality, events of possible signals of drug abuse potential, along with change from baseline in laboratory safety test variables, ECGs, and vital sign measurements will be summarized by treatment group. (revised per Amendments 01 and 06)

Other Analyses

MRI (including vMRI and fMRI) sequences will be collected for all subjects at 12 and 24 months per the Schedule of Assessments. vMRI data will be analyzed at the Screening Visit and at Visits 9 and 13 (12 and 24 months of treatment). QC and normalization procedures for measurements of the

whole brain, total ventricular volume, and right and left hippocampal volumes will be based on a validated algorithm and conducted in the same central laboratory. Additional analysis of regions of interest and cortical thickness may also be performed.

Extension Phase (revised per Amendment 06)

Primary Endpoint

- Safety endpoints: AE, vital sign, ECG, physical examination, neurological examination, laboratory safety test, suicidality assessment, events of possible signals of drug abuse potential, and MRI safety parameters

Secondary Endpoints

- Changes from Core Study baseline in CDR-SB, ADCOMS, MMSE, FAQ, ADAS-cog14, and ADAS-cog14 Word List (immediate recall and delayed recall)
- Time to conversion to dementia for subjects who were not clinically staged as dementia at Core Study baseline based on clinical diagnosis

Biomarker Endpoints

- Changes from Core Study baseline in:
 - Brain amyloid and tau PET levels
 - Total hippocampal volume as measured by vMRI
 - fMRI parameters as appropriate
 - CSF t-tau, p-tau and amyloid beta ($A\beta(1-42)$) levels
 - Plasma and CSF amyloid beta ($A\beta(1-x)$)
 - CSF biomarkers of AD (eg, NFL, VILIP1, YKL-40, and Ng)
 - Blood biomarkers of AD (eg, NFL, VILIP1, YKL-40)

Exploratory Endpoints

- Changes from Core Study baseline in NPI-10 and if available NPI-12
- Proportion of subjects who receive increase and/or initiation of other AD pharmacotherapies

Extension Phase Analysis Sets

The analysis sets defined in the Core Study will also be used for the analyses in the Extension Phase, which include: Safety, FAS, PPS, and PD Analysis Set.

Safety Analyses

Safety analysis will be performed similarly to analyses in the Core Study. The Core Study baseline will be used for subjects who are randomized to elenbecestat initially, the Extension Phase baseline will be used for subjects who are randomized to placebo but receive elenbecestat during the Extension Phase. The incidence of AEs (including changes from baseline in physical and neurological examinations, and dermatological assessments), out-of-normal-range laboratory safety test variables, abnormal ECG findings, out-of-range vital signs, suicidality (C-SSRS), and changes from baseline in laboratory safety test variables, ECGs, safety MRI, vital sign measurements will be summarized by using descriptive statistics.

Efficacy Analyses

The following efficacy endpoints will be summarized by descriptive statistics and graphs:

- Changes from baseline in CDR-SB, ADCOMS, MMSE, FAQ, ADAS-cog14, and ADAS-cog14 Word List (immediate recall and delayed recall)
- Time to conversion to dementia for subjects who were not clinically staged as dementia at

Core Study baseline based on clinical diagnosis

- Change from baseline in NPI-10 and NPI-12
- Proportion of subjects who receive an increase and/or initiation of other AD pharmacotherapies

A delayed-start analysis (Liu-Seifert et al., 2015) will be performed for each efficacy endpoint at various scheduled visits in the Extension Phase. In addition, the MMRM model will be used to analyze the above endpoints where appropriate.

Biomarker Analyses

The following biomarker endpoints will be summarized by descriptive statistics and graphs:

- Change from baseline in amyloid PET SUVR
- Change from baseline in tau PET signal
- Change from baseline in total hippocampal volume as measured by vMRI
- Change from baseline in the preservation of connectivity as measured by fMRI
- Change in baseline in t-tau, p-tau, A β (1-42) and A β (1-x) in CSF
- Change from baseline in A β (1-x) in plasma
- Change from baseline in exploratory biomarkers eg, NFL, VILIP1, YKL-40, and Ng in CSF and plasma

A delayed-start analysis and MMRM model will be used to analyze these biomarker endpoints. The relationship between efficacy endpoints and biomarker endpoints will be explored using correlation analysis.

Interim Analyses

This is a fixed design. There is no interim analysis of efficacy and no alpha spending before final analysis. However, a futility analysis is planned when approximately 30% subjects in the combined 2 studies (E2609-G000-301 and E2609-G000-302) have had an opportunity to complete the 24-month visit of the Core Study by the interim cutoff date. The sponsor may stop the trial for futility with nonbinding futility boundary calculated using conservative O'Brien-Fleming boundary of Lan-DeMets alpha spending function with 30% information based on completers. If the actual percent information of the futility analysis is different from 30%, the futility boundary will be recalculated using the actual percent information at the time of the futility analysis. A blinded sample size re-estimation through estimated standard deviation based on blinded data before the completion of enrollment, will be performed if there is an indication that sample size assumptions need to be changed. This blinded sample size re-estimation could be performed based on signals from external studies or based on review of blinded data from this study before completion of enrollment. The standard deviation of the primary endpoint was originally estimated based on data from the ADNI study. It is possible that the standard deviation for the same endpoint in clinical trials may be larger than that from this observational study. (revised per Amendment 06)

Sample Size Rationale

The sample size for this study is estimated for comparison of elenbecestat versus placebo with respect to a pooled analysis of studies E2609-G000-301 and E2609-G000-302 for the change from baseline in CDR-SB at 24 months. Based on the available data from the placebo group in Study BAN2401-G000-201 (a recently completed study with a comparable subject population), the mean and the standard deviation of the change from baseline in CDR-SB at 24 months in the placebo group are assumed to be 1.46 and 2.05, respectively, instead of 1.75 and 2.05, which are originally assumed by

the available data from ADNI (of amyloid positive, MMSE equal or greater than 24, late MCI [global CDR=0.5, CDR memory box \geq 0.5]). Therefore, assuming a 25% reduction in the mean change from baseline CDR-SB at 24 months for elenbecestat compared to placebo with common standard deviation of 2.05 and 30% dropout rate, a total sample size of 1900 subjects, 950 subjects in each treatment group, will be required to detect the treatment difference between elenbecestat and placebo using a 2-sample t test with 90% power at a significance level of 2 sided alpha =0.05.

The pooled data from 2 studies (E2609-G000-301 and E2609-G000-302) will comprise the total sample size of approximately 1900 subjects. At least 850 subjects will be randomized in each study. (revised per Amendment 06)

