Period will last 24 months. Subjects will be randomized at Visit 2 (Day 1) to receive elenbecestat 50 mg per day or placebo administered orally, once daily (QD) in the morning with or without food. During Visit 2, the subject will complete additional baseline assessments before receiving the first dose of study drug: MMSE, CDR, ADAS-cog14, FAQ, and NPI-10. Inclusion and exclusion criteria will be reviewed again, together with concomitant medications and assessment of adverse events (AEs). A single 12-lead ECG will be conducted. The C-SSRS will also be administered. A baseline routine physical examination with dermatologic review, vital signs measurements, clinical laboratory testing, urinalysis using urine dipstick, and a urine pregnancy test (females of child-bearing potential only), will be performed. Additional blood samples will be taken and stored.

During the Randomization Phase all subjects will undergo assessments of cognition, daily function, quality of life, safety, PK, PD, MRI, and vMRI (including sequences for fMRI), while those subjects who consent to participate in the amyloid PET, tau PET, and/or CSF longitudinal substudies will undergo additional assessments as indicated in the protocol. (revised per Amendments 02 and 05)

The CDR will be conducted every 3 months during the Core Study; other cognitive assessment instruments will be administered every 6 months. Every 3 months, the investigator is required to confirm the clinical staging of disease (ie, dementia or nondementia). (revised per Amendment 01) This staging decision will be verified via a central review process and adjudicated if necessary (adjudication will only occur when there is a discrepancy between the clinical disease staging made by the site compared to that determined by the central review process; moreover, where adjudication is required, it will be undertaken by an independent assessor(s)). (revised per Amendment 01)

The health-related quality of life measures will be conducted every 6 months during the Core Study along with the NPI-10.

MRI scans (including vMRI and fMRI) will be performed at 12 and 24 months during the Core Study or at the Early Discontinuation (ED)/Follow-up Visit. If subjects have non-MRI compatible devices fitted during treatment, then a computed tomography scan may be utilized to assess safety, if deemed appropriate by the investigator. (revised per Amendment 06)

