- Time to worsening of CDR scores by 24 months (eg, the worsening of global CDR score is defined as an increase from baseline by at least 0.5 points on the global CDR scale on 2 consecutive scheduled visits at which global CDR is undertaken) in the combined studies
- Time to conversion to dementia by 24 months for subjects who were not clinically staged as dementia at Baseline based on clinical diagnosis in the combined studies (revised per Amendment 01)
- Change from baseline in CDR-SB at 27 months (ie, 24 months of treatment plus 3 months posttreatment follow-up) in the combined studies (revised per Amendment 01)
- Change from baseline in ADAS-cog14, MMSE, and FAQ at 24 months in the combined studies
- Change from baseline in ADAS-cog14 Word List (immediate recall and delayed recall) at 24 months in the combined studies (revised per Amendment 01)

Biomarker Endpoints

- Change from baseline in tau PET signal at 24 months (revised per Amendment 05)
- Change from baseline in CSF biomarkers t-tau and p-tau at 24 months
- Change from baseline in CSF amyloid biomarkers $A\beta(1-42)$, and $A\beta(1-x)$ at 24 months (revised per Amendment 04)
- Change from baseline in plasma amyloid biomarker eg, $A\beta(1-x)$ at all assessments (revised per Amendment 06)
- Change from baseline in potential plasma and CSF biomarkers of AD (eg, NFL, VILIP1, YKL-40, and Ng) (revised per Amendment 06)
- Change from baseline in total hippocampal volume at 24 months using vMRI
- Change from baseline in the preservation of connectivity on fMRI at 24 months (revised per Amendment 01)

Exploratory Endpoints

- Time to change of concomitant AD treatment (ie, dose increase and/or initiation of treatment with AChEI or memantine after randomization) by 24 months
- The proportion of subjects at 24 months who received dose increases and/or initiation of treatment with AChEI or memantine after randomization
- The rate of change over time (mean slope) based on NPI-10 item score over 24 months
- Change from baseline in NPI-10 item at 24 months
- Change from baseline in EQ-5D (subject self-reported, study partner self-reported, and

subject measured by proxy) and QOL-AD (subject and study partner) at 24 months

- Change from baseline in Zarit's Burden Interview at 24 months

Analysis Sets

- The Randomized Set is the group of subjects who are randomized to study drug.

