- The Safety Analysis Set is the group of subjects who receive at least 1 dose of study drug and have at least 1 postdose safety assessment.
- The Full Analysis Set (FAS) is the group of randomized subjects who receive at least 1 dose of study drug and have baseline and at least 1 postdose primary efficacy measurement.
- The Per Protocol Analysis Set (PPS) is the subset of subjects in the FAS who sufficiently complied with the protocol.
- The PK Analysis Set is the group of subjects with at least 1 quantifiable elenbecestat plasma concentration with a documented dosing history.
- The PD Analysis Set is the group of subjects who have sufficient PD data to derive at least 1 PD parameter.

Efficacy Analyses

The FAS will be used as the primary population for all efficacy analyses, while the PPS will be used as the supportive population.

Analyses for Primary Efficacy Endpoints

The primary analysis will be based on an intent to treat philosophy without regard to adherence to treatment. The primary analysis of the change from baseline in CDR-SB at 24 months will be performed to compare elenbecestat 50 mg per day versus placebo using a linear mixed effects model for repeated measures (MMRM) on the FAS. The MMRM model will include fixed effects of treatment group, visit, treatment group by visit interaction, baseline CDR-SB, baseline CDR-SB by visit interaction and randomization stratification variables (ie, region [7 levels], clinical dementia [yes, no], and concurrent AD medication use at randomization (Visit 2) [yes, no]). *ApoE4* status may be included in the model if appropriate. (revised per Amendments 01, 02, and 06) An unstructured covariance matrix will be employed to model the covariance of within subject effect; if MMRM fails to converge then a covariance structure with fewer parameters from the following list will be employed according to the prespecified order in the list until the MMRM converges. The list of covariance structure will include Heterogeneous Toeplitz, Toeplitz, Heterogeneous Compound Symmetry, and Compound Symmetry. This primary analysis will include all observed post baseline data of the change from baseline in CDR-SB without imputation of missing values. The treatment effect for elenbecestat versus placebo will be compared at 24 months based on MMRM model. The LS means and difference in LS means between elenbecestat treatment group and placebo, and corresponding 95% confidence interval (CI) will be presented.

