The null hypothesis is that there is no difference in the mean change from baseline in CDR-SB at 24 months between elenbecestat 50 mg per day and placebo. The corresponding alternative hypothesis is that there is a difference in the mean change from baseline in CDR-SB at 24 months between elenbecestat 50 mg per day and placebo.

The primary analysis will be repeated to minimize the impact of change in concomitant AD medications where efficacy data after initiation of new AD medications and increase of current AD medications will be censored.

The following sensitivity analysis will be conducted to evaluate the impact of missing data: the primary endpoint will be analyzed using analysis of covariance model (ANCOVA) after multiple

imputation. The ANCOVA model will include baseline CDR-SB as a covariate, with treatment group, and randomization stratification variables as factors. *ApoE4* status may be included in the model if appropriate. Additional sensitivity analyses will be performed to assess the robustness of the missing at randomization assumption in the primary MMRM model.

Subgroup analysis (eg, stratification factors and *ApoE4* status) and additional sensitivity analysis for the primary endpoint will be performed as appropriate. (revised per Amendments 01 and 06)

Analyses for Key Secondary Efficacy Endpoints (revised per Amendment 06)

The key secondary analyses will be performed only if the primary analysis is significant. The treatment effect for elenbecestat 50 mg/day versus placebo, for each key secondary efficacy endpoint, will be tested using a sequential testing procedure at a significance level of 2-sided alpha =0.05, ie, any test will start only if the test with higher hierarchical order is significant.

The change from baseline in ADCOMS at 24 months will be analyzed using the same MMRM model as the primary efficacy analysis to compare elenbecestat 50 mg per day versus placebo on the FAS, using baseline ADCOMS in the model.

The change from baseline in amyloid PET SUVR at 24 months will be analyzed using the same MMRM model as the primary efficacy analysis to compare elenbecestat 50 mg per day versus placebo on the FAS, using baseline amyloid PET SUVR in the model. The same analysis will be performed within study as key secondary efficacy endpoint analyses.

Analyses for Other Secondary Endpoints (revised per Amendment 06)

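### The missing-data sensitivity analyses inherit the FAS, so randomized subjects with no CDR after dosing enter none of them; the group is probably small and including it is a cheap improvement

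*Protocol*

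**What the plan says.** In the synopsis (Analysis Sets), repeated in Section 9.7.1.2, FAS members are the randomized subjects "who receive at least 1 dose of study drug and have baseline and at least 1 postdose primary efficacy measurement". The synopsis (Efficacy Analyses) and Section 9.7.1.6 then state: "The FAS will be used as the primary population for all efficacy analyses, while the PPS will be used as the supportive population". The per-protocol set is defined as a subset of the FAS.

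A wider set exists: "The Randomized Set is the group of subjects who are randomized to study drug". The protocol assigns no efficacy analysis to it.

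Missing data are addressed in the synopsis (Analyses for Primary Efficacy Endpoints) and Section 9.7.1.6.1. The sentence opening "The following sensitivity analysis will be conducted to evaluate the impact of missing data" introduces an ANCOVA after multiple imputation, with baseline CDR-SB, treatment and the stratification variables in the model. It is followed by: "Additional sensitivity analyses will be performed to assess the robustness of the missing at randomization assumption in the primary MMRM model". Neither sentence names an analysis set.

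**The concern.** Entry to the FAS depends on something that happens after randomization. For the primary MMRM this costs almost nothing, because a subject with only a baseline score adds no information to a model of change from baseline. The imputation analysis is different: baseline CDR-SB, arm and strata are known for these subjects, so it could include them. An analysis meant to show what missing data do to the result should not begin by setting aside the subjects who have no outcome data at all.

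The exclusion could be related to treatment. The first scheduled CDR after Visit 2 is at Visit 6, week 12 (Table 5). Section 9.3.3 requires study drug to be stopped for a suspected drug rash or a seizure, and interrupted for confirmed lymphocytopenia or severe infection. Section 7.1 lists drug rash among the events of interest in the 14-day multiple-dose study and reports falls in lymphocyte counts there. If such events led more subjects in one arm to leave without any later CDR, the sensitivity analyses would not reflect it.

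**Working it through.** **1. Which population governs.** The imputation ANCOVA and the missing-at-random checks are efficacy analyses of the primary endpoint. They name no set, so the general FAS rule applies. The one stated alternative is narrower than the FAS. On the text as written, the number of subjects without a CDR after dosing who enter these analyses is therefore zero, whatever their share.

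**2. Who is left out.** Two groups: subjects never dosed, and dosed subjects with no later CDR. To be in the second group a subject must miss all of the following that apply:
- the scheduled CDRs from Visit 6 onwards ("The CDR will be conducted every 3 months during the Core Study");
- the CDR at the early discontinuation visit (Table 5);
- the CDRs at Visits 14 and 15, 4 and 12 weeks after the last dose (Table 5; Section 9.3.3 waives the first of these when drug has been suspended for 3 weeks or more);
- the 12- and 24-month return visits for discontinuers, at which Table 5, note b, lists the CDR.

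**3. The plan's own figure.** Section 9.7.2 assumes a placebo change of 1.46, SD 2.05, a 25% reduction, 30% dropout, 90% power and two-sided alpha 0.05.
- Planned difference: 0.25 × 1.46 = 0.365.
- Per arm: 2 × (1.960 + 1.282)² × 2.05² / 0.365² gives 663; divided by 0.70 this is 948 per arm, 1896 in total. The exact t calculation gives 664, 949 and 1898. The stated 1900 reproduces, and nothing here changes it.

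**4. Illustration of size.** Let a share f of the elenbecestat arm be excluded. The documents give no value for f, so every value below is an assumption.
- If the excluded subjects get no benefit, the elenbecestat mean over all randomized subjects is (1 − f) × 1.095 + f × 1.46, where 1.095 = 1.46 − 0.365. The difference from placebo is (1 − f) × 0.365.
- f = 2%: 0.98 × 0.365 = 0.358. f = 5%: 0.95 × 0.365 = 0.347.
- The shifts are about 0.007 and 0.018 points. With about 665 evaluable per arm (950 × 0.70), the standard error is 2.05 × √(2/665) = 0.112, so they are about 0.07 and 0.16 of one standard error.
- If the same shares applied to both arms, 1900 × f = 38 or 95 subjects would be brought in.
- A harsher assumed case: 5% excluded on elenbecestat and 2% on placebo, with excluded subjects 1 or 2 points worse. The difference is 0.365 − 0.05 × 0.365 − 0.03 × 1 = 0.317, or with 2 points 0.287. The smallest significant difference is about 1.96 × 0.112 = 0.22.

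**5. What the imputation assumption does.** Under missing at random, a baseline-only subject is filled in from the model for the subject's own arm. In the setting of step 4 the elenbecestat mean stays at 1.095 and the difference at 0.365. Placebo-based imputation gives (1 − f) × 0.365. The choice of assumption moves the estimate; widening the population alone does not.

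**The case against.** The strongest reply is that the protocol has not really settled the point. The FAS is called the main population, not the only one; the imputation sentence omits the FAS while the primary MMRM and several other analyses name it; and the imputation population is detail that a statistical analysis plan, not available here, commonly fixes. This stands in part: the SAP could name a wider set. But the protocol's general rule covers every efficacy analysis and points only to a narrower alternative, so as written the FAS applies.

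Several stronger readings are tempting and should not be drawn.
- A reader might infer that anyone who leaves in the first 12 weeks without an early discontinuation CDR is lost to the FAS. Not so: a CDR at Visit 14, Visit 15 or a return visit brings a dosed subject back in.
- A reader might infer that differential early departure would go unseen. Section 9.7.1.3 tabulates subjects not treated and discontinued, by arm and with reasons. An imbalance would show there; its effect on the estimate would not.
- A reader might see a contradiction with the statement that "The primary analysis will be based on an intent to treat philosophy without regard to adherence to treatment". That statement concerns keeping data after treatment stops, which the return visits serve. It does not promise that every randomized subject is analysed.
- A reader might take the percentages above as an estimate of bias. They rest on an assumed share and an assumed absence of benefit, and the first bullet makes large shares less plausible.

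**Conclusion.** The point holds in limited form. On the stated rule, randomized subjects with no CDR after dosing are absent from the primary analysis and also from the analyses meant to test its handling of missing data, and no planned analysis shows what their absence does to the estimate. The documents do not support calling the primary result biased or the primary population wrong.

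The group is probably small. Under the assumed shares of 2% and 5% with no benefit, the planned 0.365 becomes 0.358 and 0.347, well under one standard error. Even the harsher assumed case leaves the planned effect above the significance threshold, so the matter would count mainly for a borderline result. This is a cheap improvement, not a flaw that threatens the trial.

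**What to change.** Keep the primary MMRM on the FAS. In Section 9.7.1.6.1 and the matching synopsis text:
- State that the multiple-imputation ANCOVA and the missing-at-random robustness analyses include all randomized subjects with a Visit 2 CDR-SB, analysed as randomized.
- State that at least one of these analyses uses reference-based (placebo-based) or delta-adjusted imputation for subjects without a CDR after dosing. Without this the change would barely move the estimate.
- Report the number excluded from the FAS in each arm, with reasons. The planned disposition tables supply part of this but do not count FAS exclusions.

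The cost is a sentence or two of wording and some additional imputed records. The sensitivity analysis will have a slightly wider interval and a somewhat more conservative estimate. Sample size and the primary analysis are unchanged.
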